### 3.3 DOSING DELAYS AND MODIFICATIONS

#### General guidelines for treatment modifications:

Adverse Events: All adverse events in this trial will be graded using the NCI Common Terminology Criteria for Adverse Events (CTCAE) version 4.0 - a complete listing is available at the CTEP website: <http://ctep.cancer.gov/forms/CTCAEv4.pdf>.

Dose adjustments will be made according to the guidelines below, with dose levels defined as follows:

Dose Level	Mithramycin Dose
2	50 mcg/kg
1	30 mcg/kg
-1	25 mcg/kg
-2	18 mcg/kg

Summary of dose holding/interruptions and dose de-escalation recommendations for mithramycin in case of mithramycin -related adverse events (graded according to NCI-CTCAEv4.0)

General Adverse Events	Action
Non-hematological, Grade 1 or 2 (excluding hemorrhage)	
 
Continue mithramycin therapy at full dose prescribed.
 
Apply maximum supportive care recommendations.
 
If prolonged duration of Grade 2 adverse event (<math>\geq 7</math> days) is affecting quality of life, start the next treatment cycle at DL -1.
 
If event persists and continues to affect quality of life for <math>\geq 7</math> more days following initial dose reduction, start the next treatment cycle at DL -2.
 
If events continue to persist, discontinue drug.
 

Grade 3 ALT and AST	
 
Hold mithramycin therapy until recovery to Grade <math>\leq 1</math> (up to 21 days of start of cycle).
 
If ALT and AST resolve to Grade <math>\leq 1</math> within 21 days, maintain current dose level.
 
If ALT and AST do NOT resolve to Grade <math>\leq 1</math> within 21 days, dose reduce 1 level.
 
If grade 4 ALT or AST occur in a subsequent cycle, dose reduce 1 level independent of the date of resolution.
 

Grade 4 ALT and AST	
 
Hold mithramycin therapy until recovery to Grade <math>\leq 1</math> (up to 21 days of start of cycle).
 
If ALT and AST resolve to Grade <math>\leq 1</math> within 21 days,
 

General Adverse Events	Action
	
reduce 1 level.
 
 
• If grade 4 ALT or AST occur in a subsequent cycle, dose reduce 1 level independent of the date of resolution.
 


Non-hematological, Grade 3 or 4 (excluding ALT, AST, hemorrhage and QT prolongation)
	
 
• Apply maximum supportive care recommendations. Hold mithramycin therapy until recovery to Grade <math>\leq 1</math> (up to 21 days of start of cycle) and start the next treatment cycle at the next lower dose level. Note: if patient's toxicity recovers to Grade <math>\leq 1</math> prior to day 7 of treatment cycle, dosing for that cycle may resume at one dose level lower. Dosing will stop on day 7 (example: grade 3 event occurs on day 2 of dosing and resolves by day 5; patient will be allowed to receive mithramycin on days 6 and 7 at one dose level lower.)
 
• If recurrence of adverse event after drug hold/interruptions is observed at the reduced dose, and maximum supportive care measures applied, hold drug once again until recovery to Grade <math>\leq 1</math> (up to 21 days) and start the next treatment cycle one dose level lower. Note: if patient's toxicity recovers to Grade <math>\leq 1</math> prior to day 7 of treatment cycle, dosing for that cycle may resume one dose level lower.
 
• If symptoms continue to persist at grade 3 or 4, following maximal dose reduction, discontinue drug.
 

QT prolongation, Grade 3 or 4
	
 
• Cardiology consultation will be obtained to determine whether any cardiac functional assessment is warranted or if therapy should be delayed or discontinued. When warranted, ECGs will subsequently be reviewed by the NCI consulting cardiologist.
 
• If therapy is continued, dose reduce 1 level for grade 4 events
 

Bleeding Events (hemorrhage)
	

Grade 1 events
	
 
• Continue mithramycin therapy at full dose prescribed.
 
• Apply maximum supportive care recommendations.
 


Grade 2 events
	
 
• Apply maximum supportive care recommendations. Hold mithramycin therapy until recovery to Grade <math>\leq 1</math> (up to 28 days from start of treatment cycle) and start the next treatment cycle at DL -1.
 
• If recurrence of adverse event after drug hold/interruptions is observed, and maximum supportive care measures applied, hold drug once again until recovery to Grade <math>\leq 1</math> (up to 21 days from start of treatment cycle) and start the next treatment cycle at DL -2.
 
• If symptoms continue to persist at any grade, discontinue drug.
 

Grade 3 events
	
 
• Discontinue mithramycin
 

General Adverse Events	Action
Grade 4 events	
 
Discontinue mithramycin
 

All grade 2-4 hemorrhage events will initiate full hematologic evaluations as indicated in Section 3.5.1- Coagulation Studies, as well as formal Hematology consult by [name] or one of his designates	
Hematological Adverse Events	
Grades 1 and 2 events	
 
Continue mithramycin therapy at full dose prescribed. Apply maximum supportive care recommendations.
 

Grade 3 events	
 
Apply supportive care
 
If toxicities resolved to allow retreatment by day 14, resume at current dose.
 
If toxicities resolve between days 14-21 to allow retreatment (See section 3.4), resume at DL-1.
 
Following dose reduction, if toxicities persist and do not allow treatment at day 14, but are sufficiently resolved to allow retreatment by day 21, resume at DL-2.
 

Grade 4 events	
 
Apply maximum supportive care recommendations.
 
Hold mithramycin therapy until patient meets hematologic criteria for retreatment (See section 3.4) (must be within 21 days of start of treatment cycle) and start the next treatment cycle at DL -1.
 
If recurrence of hematological adverse event after drug hold/ interruptions is observed with treatment at DL-1, in the setting of maximum supportive care measures applied, hold drug once again until patient meets hematologic criteria for retreatment (See section 3.4) (must be within 28 days of start of treatment cycle) and start the next treatment cycle at DL -2.
 
If symptoms continue to persist at any grade, discontinue drug.
 

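### From 50 mcg/kg, Section 3.3 sets a lower next-cycle dose after a prolonged non-hematological Grade 2 event (25) than after a Grade 3-4 event (30)

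*Combined protocol and SAP*

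**What the plan says.** Section 3.3 (Dosing Delays and Modifications) numbers the dose levels 2, 1, -1 and -2, for 50, 30, 25 and 18 mcg/kg. Section 3.2 starts patients at 30 mcg/kg and moves those who tolerate cycle 1 to 50 mcg/kg from cycle 2.

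Two rows of the modification table matter here.

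- **Non-hematological Grade 1 or 2.** Treatment continues at full dose. If a Grade 2 event has lasted at least 7 days and "is affecting quality of life, start the next treatment cycle at DL -1" applies. If the problem continues for 7 or more "more days following initial dose reduction, start the next treatment cycle at DL -2" applies.
- **Non-hematological Grade 3 or 4** (ALT, AST, hemorrhage and QT prolongation have their own rows). Drug is held until Grade 1 or less, for up to 21 days from the start of the cycle, "and start the next treatment cycle at the next lower dose level". The next sentence begins "If recurrence of adverse event after drug hold/interruptions is observed at the reduced dose" and calls for a further hold and one more level down. If the event recovers before day 7, dosing may resume within the cycle. In the protocol's example, with onset on day 2 and resolution by day 5, the "patient will be allowed to receive mithramycin on days 6 and 7 at one dose level lower".

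**The concern.** The Grade 2 row names a fixed place on the dose scale, while the Grade 3-4 row counts steps down from wherever the patient is. The two agree from 30 mcg/kg but not from 50. At 50, the more severe event leads to the higher restart dose.

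This is not a corner case of the schedule, because 50 mcg/kg is the planned dose from cycle 2 for every patient who tolerates cycle 1. Section 1.3.3 notes that systemic toxicities tended to occur above 30 mcg/kg, so these rows may well be used at that level. What is at stake is the dose given to patients who have just had a severe event, and whether the rule is applied in the same way to each of them.

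**Working it through.** The plan gives no cumulative dose to reproduce, so the check is a lookup followed by arithmetic.

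**Inputs.** Levels 50/30/25/18 mcg/kg and the two rows above (Section 3.3); 30 mcg/kg in cycle 1 and 50 from cycle 2, seven daily doses per cycle, three cycles per course (Section 3.2).

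**1. Is DL -1 a label or a step?** It is a label. The level table lists -1 as a named level. The hematological Grade 4 row speaks of a recurrence that "is observed with treatment at DL-1, in the setting of maximum supportive care measures applied", which is a place on the scale. Where the table means a step it says so, as in the QT row: "If therapy is continued, dose reduce 1 level for grade 4 events".

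**2. Restart dose as written (mcg/kg).**

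| Dose at event | Grade 2 row, first then second step | Grade 3-4 row, first then second step |
|---|---|---|
| 50 | 25, then 18 | 30, then 25 |
| 30 | 25, then 18 | 25, then 18 |
| 25 | 25 (no reduction) at first step | 18 at first step |

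The order is inverted only from 50. The last line shows a separate gap: for a patient already at 25, the Grade 2 rule changes nothing.

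**3. Dose in the next cycle from 50** (planned 50 × 7 = 350).

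- First step: 25 × 7 = 175 (50% of planned) versus 30 × 7 = 210 (60%). 175/210 = 0.83, so the milder event gets 17% less.
- Second step: 18 × 7 = 126 (36%) versus 25 × 7 = 175 (50%). 126/175 = 0.72, so 28% less.

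**4. Course total, with the event in cycle 2** (cycle 1 + cycle 2 + cycle 3).

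- Prolonged Grade 2: 210 + 350 + 175 = 735.
- Grade 3-4, full cycle 2 given (for example, onset after the day 7 dose): 210 + 350 + 210 = 770.
- Grade 3-4, one 50 mcg/kg dose missed: 210 + 300 + 210 = 720.
- Grade 3-4, the protocol's day 2 to day 5 example, assuming the day 2 dose was given: 210 + (2 × 50 + 2 × 30) + 210 = 580.

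The Grade 3-4 total exceeds 735 only when no dose is missed.

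**5. After the fix below.** The Grade 3-4 row gives 25, 25, 18 and discontinuation for events that began at 50, 30, 25 and 18. On recurrence it gives 18, 18 and discontinuation for the first three. The amended Grade 2 row gives the same values. The Grade 3-4 course totals become 210 + 350 + 175 = 735, 210 + 300 + 175 = 685, and 210 + (2 × 50 + 2 × 25) + 175 = 535, none above the Grade 2 total.

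**The case against.** The best defence is that the two rows differ in more than dose. The Grade 3-4 row requires a hold until Grade 1 or less; the Grade 2 row re-doses without requiring resolution. A patient normally reaches 50 only after tolerating 30, so one step down returns a recovered patient to a dose already tolerated. The table does reward timely recovery elsewhere: a Grade 3 ALT/AST event that resolves within 21 days keeps its dose, and so does a hematological Grade 3 event that resolves by day 14. The first-step doses, 25 and 30, both lie within the package-insert range cited in Section 1.3.3, and the table describes itself as guidelines and recommendations.

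Much of this stands. It makes a step to 30 defensible on its own and limits the size of the point. It does not explain why the smaller cut goes with the more severe grade only from 50, when the two rows agree from 30. Nor is hold-then-step-down the table's only pattern: the hematological Grade 4 row also holds drug until retreatment criteria are met, which "must be within 21 days of start of treatment cycle) and start the next treatment cycle at DL -1". That comparison is imperfect, because the retreatment counts in Section 3.4 (platelets 75,000, ANC 1000) are below the entry counts and are not the same test as recovery to Grade 1.

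A reader might infer that worsening from Grade 2 to Grade 3 necessarily raises the next dose from 25 to 30. The text does not go that far. Once the DL -1 trigger has been met, nothing says that a later Grade 3 event cancels it, and nothing says which row governs. A restart at 30 is possible but not required. A reader might also infer that the more severe event leads to more drug overall; step 4 shows that this holds only when no dose is missed.

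**Conclusion.** The inversion is real, and small. From 50 mcg/kg the stated rules give a next-cycle dose of 25 after a prolonged Grade 2 event and 30 after a Grade 3-4 event, then 18 and 25. The gap is 35 mcg/kg per seven-dose cycle at the first step and 49 at the second. It does not arise from 30 mcg/kg.

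This rests on reading DL -1 as the named level, which the table and the hematological row support. If some staff read it as one step down instead, patients with the same event would restart at different doses, and the wording would still need correcting.

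The documents do not allow an estimate of how many patients would be affected. The primary endpoint and the two-stage decision rule in Section 8 count responses and do not depend on the restart dose. The point is worth correcting because the change is short and favours caution after a severe event.

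**What to change.** In Section 3.3, by amendment:

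- **Non-hematological Grade 3-4 row.** Key the restart to the dose at which the event began: DL -1 if it began at DL 2 or DL 1; DL -2 if it began at DL -1; discontinue if it began at DL -2. On recurrence: DL -2, or discontinue if already at DL -2.
- **The two in-cycle notes in that row.** Use the same levels, and state that an in-cycle resumption and the following next-cycle restart count as one reduction. Otherwise a patient resumed at 25 within the cycle could be read as already at DL -1 and sent to 18.
- **Grade 2 row.** Add: DL -2 if already at DL -1; discontinue if already at DL -2.

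Leave the ALT/AST and QT rows as they are. They follow their own logic, and changing them would need its own safety argument.

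The cost is a few words, with no extra patients and no statistical consequence. The downside is lower exposure after a Grade 3-4 event at 50: 25 instead of 30 (210 - 175 = 35 mcg/kg less per cycle), and at the second step 18 instead of 25 (175 - 126 = 49 less). Step wording in the Grade 2 row would also remove the inversion, but it would raise the restart dose after a prolonged Grade 2 event at 50 from 25 to 30, so it is the less cautious choice.

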### **3.2 DRUG ADMINISTRATION**

Given our recent findings pertaining to ABCB4, ABCB11, RALBP and CYP8B1 SNPs that distinguish patients who did and did not experience mithramycin-mediated hepatotoxicity on this trial, the protocol has been amended to accrue only those patients with favorable ABCB4/ABCB11/RALBP/CYP8B1 genotypes. Fourteen of these patients (7 with primary thoracic malignancies and 7 with extrathoracic malignancies metastatic to the chest) will receive mithramycin infusions during cycle 1 at 30mcg/kg per day. Those patients tolerating 30 mcg/kg infusions during the first cycle will receive subsequent cycles of mithramycin at a dose of 50 mcg/kg using the same infusion schedule. Based on the PK data obtained on this trial to date, this dose of mithramycin would be expected to produce Cmax of ~40nM and steady state levels of ~20-25nM, concentrations approximating lowest therapeutic doses in preclinical tissue culture experiments. Patients exhibiting dose-limiting toxicities during cycle 1 will receive subsequent infusions at a dose of 25mcg/kg, with dose reduction guidelines listed in section 3.3. If one or more patients in each cohort exhibit response to therapy, an additional 14 patients will be accrued to the respective cohort(s) to further define response rates Simon Second Stage). Drug administration in the Second Stage will be identical to that in the First stage.

Mithramycin will be administered intravenously via central line over 6 hours once daily for 7 days to be repeated every 21 days (+7 days/-3 days). Three cycles will constitute one course. Intravenous hydration will be provided as clinically indicated.

**Note:** At least 23 hours should elapse between the beginning of one infusion and the beginning of the next.

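### Section 3.3 mixes named dose levels with one-level steps; the two agree only at 30 mcg/kg, so the restart dose after toxicity is inconsistent at 50, 25 and 18 mcg/kg

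*Combined protocol and SAP*

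**What the plan says.** Section 3.3 introduces its table with "Dose adjustments will be made according to the guidelines below, with dose levels defined as follows" and lists 2 = 50, 1 = 30, -1 = 25 and -2 = 18 mcg/kg. There is no level 0. The rows then use two conventions.

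**Rows that name a level (DL -1 first, DL -2 later):**
- Non-hematological grade 2, lasting 7 days or more: "is affecting quality of life, start the next treatment cycle at DL -1".
- Grade 2 hemorrhage, first event: a hold ("up to 28 days from start of treatment cycle) and start the next treatment cycle at DL -1"). On recurrence: "up to 21 days from start of treatment cycle) and start the next treatment cycle at DL -2".
- Grade 4 hematological events, and grade 3 hematological events that resolve between days 14 and 21.

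**Rows that step down from the current dose:**
- Other non-hematological grade 3-4 events (ALT/AST, hemorrhage and QT prolongation excluded): "start the next treatment cycle at the next lower dose level".
- Grade 4 ALT/AST: one level down after recovery within 21 days and, if grade 4 occurs in a later cycle, "dose reduce 1 level independent of the date of resolution". Grade 3 ALT/AST drops one level only if it has not recovered within 21 days.
- Grade 4 QT prolongation, if treatment continues.

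Section 3.2 sets the doses to which these rows apply. Patients who tolerate cycle 1 at 30 mcg/kg "will receive subsequent cycles of mithramycin at a dose of 50 mcg/kg using the same infusion schedule". Patients with a dose-limiting toxicity in cycle 1 continue at 25 mcg/kg.

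**The concern.** A rule that names a level and a rule that steps down from the current dose give the same result only when the patient is one level above the named level. With 50 mcg/kg in the table as level 2, and with some patients at 25 from cycle 2, that condition fails on both treatment paths that Section 3.2 plans.

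Two consequences stand out. Among non-hematological events at 50 mcg/kg, the size of the cut runs opposite to the grade, and no reason is given. At 25 mcg/kg, a row whose own wording treats the move to DL -1 as a first reduction produces no reduction.

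This is an operative safety instruction. Section 1.3.3 describes hemorrhage as the most profound toxicity seen with the drug and as dose-related. Two careful readers could restart the same patient at different doses. Section 7.2.1 requires every protocol deviation to be reported, yet the text does not settle which of the two restarts would be one.

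**Working it through.** **Inputs.** The four levels and the row rules come from Section 3.3. The doses in use from cycle 2 (50 or 25 mcg/kg) come from Section 3.2. The plan states no figure of its own to reproduce on this point.

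**Step 1: apply both conventions to each current dose.** Percent change = 100 × (new − current) / current.

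| Current dose (mcg/kg) | Named level DL -1 (= 25) | One level lower |
|---|---|---|
| 50 | 25: (25−50)/50 = −50% | 30: (30−50)/50 = −40% |
| 30 | 25: (25−30)/30 = −16.7% | 25: −16.7% |
| 25 | 25: (25−25)/25 = 0% | 18: (18−25)/25 = −28% |
| 18 | 25: (25−18)/18 = +38.9% | no level below |

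The conventions coincide at 30 mcg/kg only.

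**Step 2: place the rows at 50 mcg/kg.**
- Non-hematological grade 2, 7 days or more, affecting quality of life: 25 (−50%).
- Non-hematological grade 3-4 (outside the exclusions), or grade 4 ALT/AST: 30 (−40%).
- Grade 4 hematological: 25 (−50%). Grade 3 hematological: current dose if resolved by day 14, or 25 if resolved on days 14-21. There is no inversion within this group.
- Hemorrhage: grade 2 leads to 25 and grade 3-4 discontinues. There is no inversion here either.

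**Step 3: place the rows at 25 mcg/kg**, reached after a cycle 1 dose-limiting toxicity. A first grade 2 bleed, a first prolonged grade 2 event or a first grade 4 hematological event is sent to DL -1, which is 25 (0%). A non-hematological grade 3-4 event goes to 18 (−28%).

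**Step 4: 18 mcg/kg.** A patient at 25 who has a non-hematological grade 3-4 event moves to 18. If that patient then has a first grade 2 bleed, DL -1 read literally means 25 (+38.9%).

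**Step 5: test the other reading.** Suppose DL -1 meant one level below the current dose. Then at 50 both the prolonged grade 2 event and the grade 3-4 event lead to 30 (−40%), and a first grade 2 bleed at 25 leads to 18 (−28%). Both anomalies vanish, so they come entirely from mixing the conventions. This shows the effect of the reading and takes no view on which is right.

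**Step 6: recovery windows (secondary).** Grade 2 bleeding allows 28 days at the first event and 21 at recurrence. Grade 4 hematological events allow 21 days first and, at recurrence, "must be within 28 days of start of treatment cycle". The two orders are opposite and no reason is given.

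**The case against.** The best defense is that DL -1 was meant as one level below the current dose, that Section 3.3 calls its contents guidelines and recommendations, and that Section 3.6.1 lets the investigator stop treatment for excessive toxicity or in the patient's interest. On that view, the zero cut at 25 is a case nobody addressed, not an instruction to re-treat unchanged. The grade 2 row's reference to the move as an initial reduction supports this view of intent. The wording does not. In the table, -1 is the label for 25 mcg/kg; the grade 4 hematological row speaks of a patient being treated at DL-1; and the other rows have separate words for a relative step. If the relative reading was intended, the text still has to say so.

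Several stronger readings are tempting, and the documents do not support them:
- **That every grade 3-4 event at 50 takes a smaller cut than a grade 2 event.** Grade 3-4 hemorrhage discontinues the drug, grade 4 hematological events go to 25, and the grade 2 rule needs both 7 days' duration and an effect on quality of life.
- **That a bleed at 25 draws no response.** A grade 2 bleed brings a hold until grade 1 or less, maximum supportive care, a full hematologic evaluation and a formal consult. Recurrence goes to 18.
- **That the 8 of 12 patients with dose-limiting transaminitis (Section 1.3.4) predict how many will be at 25.** They were enrolled without regard to genotype, accrual is now restricted because of that toxicity, and the text available does not define a cycle 1 dose-limiting toxicity. Section 1.3.4 also reports no bleeding and no myelosuppression in those 12.
- **That a 28-day window cannot fit a 21-day cycle.** Section 3.2 allows +7 days, and 21 + 7 = 28. The day-21 condition in Section 3.4 is written for the next course, although the hematological rows refer to that section.
- **That the primary response analysis is affected.** Section 8 counts best response per cohort whatever dose was received, and the two-stage boundaries do not change.

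**Conclusion.** The point holds in a narrow form. Followed as written, Section 3.3 contradicts itself at the two doses Section 3.2 prescribes from cycle 2. At 50 mcg/kg, a prolonged grade 2 non-hematological event costs 50% of the dose, while a grade 4 ALT/AST event or another non-hematological grade 3-4 event (hemorrhage and QT prolongation excluded) costs 40%. At 25 mcg/kg, a first grade 2 bleed, prolonged grade 2 event or grade 4 hematological event costs 0%; at 18 mcg/kg the same wording would raise the dose by 39%.

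These figures assume that DL -1 and DL -2 are the levels listed in the table, which is the reading the text supports. They concern the restart dose only, since the holds and work-up are not in doubt. How many patients would meet these situations cannot be derived from the documents. The opposite order of the recovery windows is an unexplained inconsistency of lesser weight.

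**What to change.** Reconcile Sections 3.2, 3.3 and 3.4:
- Write every row of the Section 3.3 table in one convention, with a single meaning from each of the four levels.
- State explicitly what each row means for a patient already at 25 or 18 mcg/kg, including rows that step down when no lower level exists.
- Check the order of the recovery windows for grade 2 bleeding and grade 4 hematological events. Either align them or give the reason for the difference, and say how they relate to the +7-day allowance in Section 3.2 and the day-21 condition in Section 3.4.

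Which dose and which window apply is for the investigators to decide. The cost is a wording amendment, mainly to one table, with no added patients, procedures or analyses.

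### Section 3.3 restarts at a fixed 25 mcg/kg after a first bleeding, hematological or prolonged Grade 2 event, so a patient already at 25 gets no reduction and one at 18 has no usable rule

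*Combined protocol and SAP*

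**What the plan says.** Section 3.3 lists four dose levels: DL 2 = 50, DL 1 = 30, DL -1 = 25 and DL -2 = 18 mcg/kg. The adverse-event table then uses two kinds of instruction.

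**Fixed level after a first event**
- Grade 2 bleeding: hold until Grade 1 or less, "up to 28 days from start of treatment cycle) and start the next treatment cycle at DL -1".
- Grade 4 hematological: hold until the retreatment criteria are met, "must be within 21 days of start of treatment cycle) and start the next treatment cycle at DL -1".
- Prolonged Grade 2 non-hematological: if the event "is affecting quality of life, start the next treatment cycle at DL -1".
- Grade 3 hematological: "If toxicities resolve between days 14-21 to allow retreatment (See section 3.4), resume at DL-1". If it resolves by day 14, the current dose is kept.

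**Relative step**
- ALT/AST: for example, Grade 3 elevations that have not settled "within 21 days, dose reduce 1 level".
- Other Grade 3-4 non-hematological events: hold "and start the next treatment cycle at the next lower dose level".
- Grade 4 QT prolongation: one level down if therapy continues.

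In the fixed rows DL -2 is a second step. For bleeding it follows a recurrence: "up to 21 days from start of treatment cycle) and start the next treatment cycle at DL -2". For Grade 4 hematological events it follows a recurrence while on DL -1. In the other two rows it follows persistence after a dose reduction.

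Section 3.2 adds: "Patients exhibiting dose-limiting toxicities during cycle 1 will receive subsequent infusions at a dose of 25mcg/kg". It points to 3.3 for any further reduction.

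**The concern.** In the fixed rows the instruction lowers the dose only for a patient at 50 or 30 mcg/kg. The protocol itself places some patients at 25 mcg/kg because they did not tolerate more, and 3.3 is the rule it names for them. If such a patient then has a first Grade 2 bleed or a first Grade 4 hematological event, the table restarts at the dose that produced it. A Grade 3 non-hematological event at the same dose would lead to 18 mcg/kg.

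At stake is the safety of patients who have already shown intolerance, with a drug for which section 1.3.3 treats hemorrhage as the gravest toxicity and describes it as dose-related. The response endpoint and the two-stage decision rule are not involved.

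**Working it through.** The plan gives no figure to reproduce. The check is to apply each instruction at each dose level.

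**Inputs.** Levels 50, 30, 25 and 18 mcg/kg (3.3); seven doses per cycle (3.2).

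**Step 1. Can DL -1 mean one level down?** No. It is a defined dose, and the same table uses relative wording where a relative step is meant.

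**Step 2. How does a patient come to be at 25 mcg/kg?**
- By a dose-limiting toxicity in cycle 1 (3.2).
- By a one-level step from 30 under the ALT/AST, Grade 3-4 non-hematological or QT rows.
- By a first event in one of the fixed rows, which takes 50 or 30 to 25. A later first event in another fixed row meets the same gap.

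**Step 3. Dose change after a first event** (new dose / current dose - 1)

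| Dose at event | Fixed DL -1 | DL -1 or one level below, whichever is lower |
|---|---|---|
| 50 | 25: 25/50 - 1 = -50% | min(25, 30) = 25: -50% |
| 30 | 25: 25/30 - 1 = -16.7% | min(25, 25) = 25: -16.7% |
| 25 | 25: 25/25 - 1 = 0% | min(25, 18) = 18: 18/25 - 1 = -28% |
| 18 | 25: 25/18 - 1 = +38.9%, read literally | no lower level; needs its own rule |

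At 25 mcg/kg the difference per cycle is 7 x 25 = 175 against 7 x 18 = 126 mcg/kg.

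**Step 4. Do the second-step lines close the gap?**
- Bleeding and Grade 4 hematological rows: no. Both require a recurrence, so the patient must have the event twice before reaching 18.
- Prolonged Grade 2 non-hematological row: no. It asks for seven further days of the same event after the reduction.
- Grade 3 hematological row: arguable. It speaks of toxicities persisting after dose reduction and does not say that the reduction must have been for the same toxicity. The plainer reading is that it was, which leaves the gap. The other reading already gives DL -2.

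**Step 5. How often?** The documents do not say. In the closed cohort (1.3.4), 0 of 12 patients had bleeding or myelosuppression. The exact one-sided 95% upper bound is 1 - 0.05^(1/12) = 0.221, or 22%. That bound does not estimate this scenario:
- It concerns any such event in a cohort not selected by genotype and treated at 25-30 mcg/kg, with toxicity evaluated in cycle 1.
- The scenario is a first event after a reduction for a different toxicity, so it falls in later treatment.
- The bound leaves out prolonged Grade 2 non-hematological events altogether.

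**The case against.** **The fixed level may be deliberate.** Section 1.3.3 says most later studies used 25 mcg/kg/day and that toxicity tended to appear above 30. The table also keeps the current dose in places, so it does not promise a reduction after every event. But it does so only for events that resolve promptly: Grade 3 ALT/AST within 21 days and Grade 3 hematological events by day 14. That does not show that 25 to 25 is intended after a Grade 2 bleed or a Grade 4 hematological event.

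**Other protections exist.** These stand, and they lower the weight of the point:
- Supportive care applies in all four rows, and treatment waits for recovery in the bleeding and hematological rows.
- Section 3.4 sets platelet and neutrophil thresholds, and blood counts are daily during dosing in cycles 1 and 2.
- Grade 2-4 bleeds trigger a hematologic work-up and a Hematology consult, although the work-up cites 3.5.1, which lists no coagulation tests.
- Grade 3-4 bleeding ends treatment.
- The table's contents are called recommendations, and 3.6.1 allows removal for excessive toxicity or in the patient's best interest.

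None of these supplies a lower dose.

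**The route is narrow.** This is also fair. Patients who tolerate cycle 1 go to 50, and a relative step from there lands on 30. Reaching 18 takes more still.

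**Stronger readings to resist.** A reader might infer that patients at 18 will be escalated to 25. The literal text says so, but an investigator is unlikely to do it under a table about de-escalation; in practice there is no usable instruction. A reader might also infer a known excess of bleeding at 25 over 18. The 5.4% of 1150 patients in 1.3.3 is for 30 mcg/kg/day or more. The fatal bleed at 25 ug/kg in Appendix 1 followed a day 1 dose in a hypercalcemia study and came from a duodenal ulcer. It shows that 25 is not free of risk, but says nothing about 25 against 18.

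**Conclusion.** The point holds. It is firm for the Grade 2 bleeding, Grade 4 hematological and prolonged Grade 2 non-hematological rows. It holds for the Grade 3 hematological row (resolution on days 14-21) only on the plainer reading of that row. A first event at 25 mcg/kg brings a 0% change where one level down would bring -28%, and an event at 18 mcg/kg has no workable rule.

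The conclusion assumes that dose-level labels carry their defined meaning and that recurrence and persistence refer to the same event. The number of patients affected is unknown and probably small, and the clinical gain from 18 over 25 cannot be quantified from the documents. This is a safety rule that should be repaired at the next amendment. It does not threaten the trial's primary analysis.

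**What to change.** In the four rows, replace the first-event restart at DL -1 with: *DL -1 or one level below the dose at which the event occurred, whichever is lower*. This leaves 50 to 25 and 30 to 25 as they are and gives 25 to 18. It also removes the ambiguity in the Grade 3 hematological row.

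Add a rule for an event at DL -2:
- Grade 2 bleeding or a Grade 4 hematological event: discontinue.
- A first prolonged Grade 2 non-hematological event, or a Grade 3 hematological event resolving on days 14-21: do not raise the dose; continue at DL -2 and discontinue if the event persists or recurs. Mandatory stopping here would be hard to justify, for example in a responding patient.

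**Cost.** A clause in four rows plus the DL -2 rule. Hold limits, 3.4, sample size, schedule and assessments do not change. The downside is slightly lower exposure or earlier stopping in a few patients. Earlier stopping could occasionally cost evaluability for response, because 8.2 requires a full course and the accrual ceiling leaves little slack: 57 - 42 - 12 = 3 patients.
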